7.1. Standards for the clinical trial

To allow for 73 evaluable subjects at 6 months follow up, a total of up to 90 patients will be enrolled (the statistical power of the study is provided in a section below, dedicated to statistical analysis). Each center will be offered to supply a sufficient number of patients as study subjects (up to 15 patients). Approximately half of these patients will be with lipohypertrophy (LH), and half will be without. Ideally, each center should recruit half of their patients with and half of their patients without LH. The Sponsor will monitor if the overall balance of 50%/50% is maintained

and will advise study centers accordingly. The main goal is to have an equal distribution across the study, not necessarily per site, however, each study center should have at least a distribution of 1/3 versus 2/3 in each group. The optimal injection technique and choice of needle length is based on the Russian Procedural Guidelines on injection techniques and infusions used in the treatment of diabetes mellitus [1]. These Guidelines, in turn, are based on recently published international guidelines by the Forum for Injection Technique Therapy Expert Recommendations (FITTER) [5].

7.2. Outcome measures for the clinical trial

- Reduction in glycated hemoglobin (HbA1c, in %);
- Insulin total daily dose (TDD);
- Incidence of hypoglycemia;
- Incidence of severe hypoglycemia (which require assistance by others);
- Change in Blood Glucose levels (measured by BGM)
- Correct alternation of injection sites;
- Cases of repeat needle use;
- Change of lipohypertrophy, its size (length and width in mm) and localization (if applicable);
- Cases of injection into lipohypertrophy areas (if applicable);
- Patients' quantitative experience with the use of distant video lessons.
- Quality of Life assessments (EQ-5D)

7.3. Inclusion/exclusion criteria.

The selection of patients will not be influenced by race, religion, socio-economic and other factors. Approximately 50% of the subjects to be enrolled will have lipohypertrophy areas and 50% of the subjects will not.

Inclusion criteria:

1. Type 1 or type 2 diabetes mellitus;
2. Patients (male and female) of 18 years of age and over;
3. At least 1 year of experience with insulin self-administration;
4. Use of insulin pen for insulin injections.
5. HbA1c > 7.5% measured at study entry or maximally 30 days prior to study entry..
6. BMI below 40 kg/m² at study entry.
7. Daily self-control of blood glucose level;
8. Access to the internet for watching video lessons.
9. Only outpatients are eligible for the study.
10. Availability of the patient's signed informed consent for inclusion in the study.

Exclusion criteria:

1. Pregnant women or women planning to become pregnant during the time of study, breastfeeding women;
2. Subjects using an insulin pump;
3. Those using treatment with a GLP-1 receptor agonists alone;
4. Subjects not fluent in Russian (reading and writing).
5. Patients at high risk for ketoacidosis and/or hyperglycemia.
6. Psychic, physical or any other reasons hampering patient participation in the study (based on the reasonable opinion of the physician-investigator).

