- 1) *Hemorrhages and hematomas.* Sometimes during an injection, the needle may damage blood vessels, causing hemorrhages or hematomas. Changes in needle length or other injection parameters do not seem to influence the rate of occurrence of bleeding or hematomas, although, according to some data, these complications may occur less frequently when short needles are used. Pressing on the injection site for 5-10 seconds should stop the bleeding [1].
- 2) *Leakage of the medication from the injection site.* This can occur due to the following reasons:
 - a) a one-time injection of a large insulin dose. In some cases, it would be preferable to divide large insulin doses into two doses and inject them one after another [1].
 - b) individual skin properties (dermal structure) and its age-related changes may be the cause of medication leakage following an injection [1].
- 3) *Pain.* Injections of insulin and GLP-1 receptor agonists do not usually cause pain, except for cases when the needle damages nerve ending fibers, which is a fairly rare event. However, some patients respond to injections in a rather sensitive way and describe their sensations as painful ones. Patient discomfort during injections was carefully studied and is attributed to three key factors: needle length, needle diameter and injection setting [1].

The benefit provided by this study is the demonstration of the fact that proper insulin injection technique used by patients is a prerequisite for achieving good glycemic control of diabetes, reducing the variability in the absorption of insulin preparations, and obtaining the optimal effect of their use [1]. Also, we expect that the proper technique of insulin injections will help to reduce the risks of injections: hemorrhages, hematomas cases and pain.

6. Objectives of the clinical trial and the hypotheses to be tested

The study aims at verifying the effect of teaching the optimal technique of insulin injection using the multimodal individual approach, supplemented with a personalized remote platform for the education of diabetic patients who are on insulin therapy, with regard to the clinical outcomes and essential skills necessary for managing diabetes.

This is a prospective study conducted in Russia, with a subsequent progress review after a 6-month follow-up to assess the correctness of insulin injection technique. The study design represents a “before” and “after” comparison, where the patient is left under

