	2 Obtaining the informed consent	2 Evaluate current level of glycemic control and cases of hypoglycemia	2 Evaluate current level of glycemic control and cases of hypoglycemia.	2 Evaluate current level of glycemic control and cases of hypoglycemia.
	3 Assignment of participant identification number (code)	3 Find out about current level and frequency of measuring blood glucose and insulin TDD.	3 Examine injection sites and injection technique, size and localization of lipohypertrophy	3 Examine injection sites and injection technique, size and localization of lipohypertrophy
	4 Fill in the questionnaire, enter data regarding HbA1c and insulin TDD. Note: the HbA1c value may be measured at screening or the latest measured value (max. 30 days prior to screening) may be taken.	4 Make sure that the patient follows the recommended injection technique, correctly alternates injection sites and avoids injections into sites of lipohypertrophy. Remind the patient to use the BGM and complete the diary.	4 Enter data regarding possible AE	4 Collect diary and review completion
	5 Examine injection sites and injection technique, size and localization of lipohypertrophy (if applicable).	5 Enter patient's answers in the interim control form	5 Review diary completion	5 Request patient to complete the EQ-5D questionnaire
	6 Evaluate current level of blood glucose and cases of hypoglycemia.	6 Remind patient about next personal visit	6 Download the data from the BGM to a PC for further statistical analyses.	6 Arrange subsequent medical follow-up for the patient, if required
	7 Carry out personalized training on correct injection technique	7 Enter data regarding possible AE	7 Provide new supply of BD Micro-Fine Plus 4 mm 32G needles (3 months' supply) and additional strips and lancets for BGM.	7 Release patient from participation in the study (fill in Exit from study form).
Follow-up visits – visit №2, and 4 (by phone) in 45 and 135 days +/-10 days after visit 1		Follow-up visit – visit №3 (personal) in 90 days +/-10 days after visit 1		Visit 5 (personal, final) in 180 days +/-10 days after visit 1

8 Familiarize patient with distance education resource and recommend independent studies using video lessons		8 Schedule the HbA1c test and next personal visit in 90 days. Schedule next telephone follow up (visit 4)	8 Download the data from the BGM to a PC for further statistical analyses.
9 Request patient to complete the EQ-5D questionnaire			9 Enter data regarding possible AE

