10 Provide patient with required supply of BD Micro-Fine Plus 4 mm 32G needles (3 months' supply).			10 Collect the BGM from the patients. Complete the log forms
11 Schedule the HbA1c test and next personal visits in 90 and 180 days, and over-the-phone visits for interim control in 45 and 135 days.			
12 Provide patients the diary and a Blood Glucose Meter (BGM) with strips and lancets (3 months' supply). Explain how to complete the diary and use BGM.			
13 In a week +/-2 days after the screening visit, the investigator must ascertain if patient viewed recommended lessons.			

Visit № 1 – screening visit (personal visit).

1. For study purposes, prior to patient enrolment a physician will interview the patient about his/her condition in order to evaluate the effectiveness of current practices in terms of injection technique, the finding of gaps and possibilities for their improvement. Depending on the results of such an evaluation, the investigator will offer the patient familiarization with the corresponding distance learning modules.
2. Information about study participation is provided, and the informed consent form is signed.
3. Collection of the patient's demographic data and medical history data is carried out. The patient undergoes a physical examination to make sure that he/she meets the inclusion/exclusion criteria. A urine pregnancy test must be done for the childbearing potential female patients.
Examination of injection sites and injection technique is performed. The presence of lipohypertrophy is determined, and lipohypertrophy areas are marked on the diagram, indicating their number and size.
4. A physician makes an arrangement for the glycated hemoglobin test (HbA1c), which is carried out in the laboratory of the center participating in a given clinical trial at investigator's place of work.. To verify the inclusion criteria, the HbA1c value may be measured at screening or the latest measured value (max. 30 days prior to screening) may be taken. The result should be entered in the eCRF.
5. The current level of blood glucose and cases of hypoglycemia will be evaluated during the visit and the patient will be asked about his/ her condition and data will be completed in the eCRF.
6. The insulin dose of the day prior to the visit (basal and boluses) will be captured in the eCRF.

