13. Patients are instructed how to use the BGM and its accessories, how to complete the patient's diary. BGMs will be calibrated if needed and the date and time will be set correctly. Patients will be recommended to make at least 4 measurements of glucose per day by the provided BGM regardless of the type of diabetes: 3 before meals (one of which is before breakfast) and one measurement before bedtime. More measurements may be performed in accordance with clinical practice. The recommended measurements as listed above should be performed during the following time periods:

- a. within 2 weeks after screening,
- b. the last 2 weeks before the visit of the 3rd month, and
- c. the last 2 weeks before the visit of the 6th month.

The rest of the time, the patient may measure the level of glucose in the blood in accordance with accepted clinical practice.

During the same 2 weeks periods the patient is asked to complete the diary with basal and bolus insulin doses on a daily basis. Also, the patient has to complete the diary with all episodes of hypoglycemia.

14. The next meeting with the physician-investigator is scheduled in 90-100 days (visit № 3), as well as the interim visits, which include phone contacts in 45 +/-10 days (visit № 2) and in 135 +/-10 days (visit № 4).
15. A preliminary scheduled blood test for glycated hemoglobin takes place in 90 +/-10 days as well as in 180 +/- 10 days after the screening visit, to be carried out in the laboratory of the center participating in a given clinical trial at the investigator's place of work. The test must be done not sooner than a week before the study completion visit or on the day of the completion visit.
16. The Investigator informs the patient they have to visit the investigator before the next scheduled personal visit in case they do not have sufficient strips. Also, the patient can visit the investigator personally instead of the phone visit if the patient realizes they do not have enough strips to cover the period until the next scheduled personal visit. In this case, the patients have to bring the diary and his BGM for the visit and the Investigator will download the data from BGM and return it back to the patient. The diary will be kept by the investigator and the patient will receive the new diary. The patient also will receive the required number of strips in amount enough to the next scheduled personal visit.

1-week visit (optional, phone).

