Quality of Life questionnaire (EQ-5D)	X			X
Patient examination for lipohypertrophy	X		X	X
Glycated hemoglobin (HbA1c)	X		X	X
Collect information on occurrences of hypoglycemia	X	X	X	X
Patient education classes, video lessons scheduling, provision of needles	X			
Control of video lessons' viewing	X	X	X	X
Exit from the study				X
Collection of adverse event information		X	X	X

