5.2.2 HbA1c

For HbA1c, analysis will be performed using linear mixed effect models to evaluate the effect of personalized teaching of the optimal insulin injection technique in conjunction with the use of disposable BD Micro-Fine Plus 32G pen needles on the response. In the model, subject will be a random effect, time period (baseline, 3 months or end of study) and lipohypertrophy will be fixed effects. Two-way and three-way interactions between fixed effects will be investigated. Only significant interactions will be included in the model. Models will be used to compute estimated mean, difference between baseline and end of study, and corresponding two-sided 95% CI for responses of interest.

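### Patients are selected on HbA1c > 7.5% and the single-arm primary result is the later change in HbA1c, so part of any fall is regression to the mean; the baseline value is also not defined

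*Protocol*

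**What the plan says.** **Selection and outcome.** Protocol 7.3 criterion 5, repeated in SAP 2.2, requires "HbA1c > 7.5% measured at study entry or maximally 30 days prior to study entry". The primary endpoint in SAP 2.5.1 is the reduction in that same variable at 6 months. Protocol section 7 states a single arm, and section 6 says: "The study design represents a “before” and “after” comparison".

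**Primary analysis.** SAP 5.2.2 fits a linear mixed model with a random subject effect and fixed effects for time period and lipohypertrophy. It then states: "Models will be used to compute estimated mean, difference between baseline and end of study, and corresponding two-sided 95% CI". The same paragraph gives the model's purpose as evaluating the effect of the personalized teaching together with the needles. SAP 2.6 sets no acceptance criteria. SAP 5.2.9 treats p-values below 0.05 as statistically significant.

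**Baseline value.** Table 2 of the protocol schedules HbA1c at Visits 1, 3 and 5, matching the three time levels in the SAP, so Visit 1 is the implied baseline. The texts on what may be entered there differ:
- Protocol 7.5, Table 1, Visit 1 item 4: "Note: the HbA1c value may be measured at screening or the latest measured value (max. 30 days prior to screening) may be taken". No laboratory is given for the older value.
- Protocol 7.5, Visit 1 item 4: "A physician makes an arrangement for the glycated hemoglobin test (HbA1c), which is carried out in the laboratory of the center", followed by "To verify the inclusion criteria, the HbA1c value may be measured at screening or the latest measured value (max. 30 days prior to screening". This can be read as a center-laboratory test for everyone, with the older value used only for eligibility.
- Protocol 7.5, Visit 1 item 15: the 3- and 6-month tests are "to be carried out in the laboratory of the center participating in a given clinical trial", and the final one is taken no more than a week before the completion visit.

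**The concern.** Cutting the outcome off from below at entry makes the baseline mean too high relative to where the same patients would later settle. The resulting fall runs in the hypothesised direction, and no control arm exists to reveal it. The confidence interval does not show it either, because the interval is centred on the biased value.

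With no acceptance criterion, what is at stake is the estimate and how it is read: a before-after change would be reported as the effect of teaching. Protocol 7.5 (Visit 1 item 7) and 7.6 also allow insulin dose to change during the study, which is a second reason why the change is not the effect of training alone.

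The undefined baseline is a separate, smaller matter. An older value may come from a different laboratory and a different interval before training than the follow-up tests are held to.

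**Working it through.** **1. The plan's own figure.** Inputs from Protocol 10.1: fall 0.4, SD of paired differences 1.2, power 80%, alpha 0.05. A two-sided one-sample t-test (noncentral t) gives n = 73 with power 80.2%, so the stated 73 is reproduced. The 95% CI half-width at n = 73 is t(0.975, 72) × 1.2/√73 = 1.993 × 0.1404 = 0.28.

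**2. The model does not remove the artefact.** With complete data at three visits, the random-intercept contrast between baseline and end of study equals the mean paired difference. Simulating 4,000 trials (n = 73, correlation 0.7, mean 8.5, SD 1.6) gave 0.215, the same as the formula below. The lipohypertrophy term does not alter the time contrast.

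**3. Formula when the qualifying value is the baseline.** Let z = (7.5 − mean)/SD and λ = φ(z)/(1 − Φ(z)).
- Artefact = (1 − rho) × SD × λ.
- Variance of the baseline in selected patients: v = SD² × (1 + zλ − λ²).
- Variance of change in selected patients = (1 − rho)² × v + SD² × (1 − rho²).

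The unselected mean and SD are not in the documents and are assumptions. The planned SD of change can be used to fix rho.

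**4. Worked case, mean 8.5 and SD 1.6.** z = −0.625, λ = 0.328/0.734 = 0.447, SD × λ = 0.715, selected mean 9.215, v = 1.333. Setting the variance of change to 1.2² = 1.44 gives rho = 0.697, since 0.303² × 1.333 + 2.56 × (1 − 0.697²) ≈ 0.12 + 1.32 = 1.44. Artefact = 0.303 × 0.715 = 0.22.

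**5. Range, rho solved the same way.**

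| Assumed mean | SD 1.2 | SD 1.5 | SD 1.8 |
|---|---|---|---|
| 8.0 | 0.39 | 0.32 | 0.27 |
| 8.5 | 0.24 | 0.22 | 0.20 |
| 9.0 | 0.13 | 0.15 | 0.15 |

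The solved rho runs from 0.41 to 0.77. This treats all of the 1.2 as within-patient variation. If part of it is variation in response to training, rho is higher and the artefact smaller: in the worked case, 0.14 at rho 0.8 and 0.07 at rho 0.9.

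**6. What drift alone would do.** At n = 73 and SD 1.2, the chance of a statistically significant fall with no training effect is 2.5% at zero drift, and 10%, 29% and 56% at drifts of 0.1, 0.2 and 0.3.

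**7. A separate Visit 1 baseline.** Let r1 be the correlation of an earlier qualifying value with the Visit 1 value (assumed 0.90 to 0.97). The artefact becomes (r1 − rho) × SD × λ, so the share removed is (1 − r1)/(1 − rho). That runs from 0.03/0.4 = 8% (r1 0.97, rho 0.6) to 0.1/0.1 = 100% (r1 0.90, rho 0.9). Patients who qualify on the Visit 1 sample gain nothing. In the worked case with rho 0.7 and r1 0.90, the overall artefact is 0.21 if no patient uses an earlier value, 0.18 if half do and 0.14 if all do.

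**The case against.** **The design is declared.** The protocol says openly that this is a before-after study, and any uncontrolled study with an entry threshold shares the problem. This stands as far as it goes: it is a limit on interpretation, and no control arm is asked for. But SAP 5.2.2 and the objectives go beyond the declared design by naming the result as the effect of teaching.

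**The 0.4 comes from internal studies of similar design.** This also stands. The assumed fall may already include the same artefact, so setting the two side by side does not show that the power calculation is wrong. It means that the power applies to the total change.

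**Readings that the documents do not support.**
- A reader might infer that the 30-day option makes regression to the mean worse. It does not: an older qualifying value used as baseline gives the same (1 − rho) form as a same-day value. It adds unequal timing and possibly a different laboratory.
- A reader might fear that patients whose Visit 1 value is 7.5% or lower would be dropped as major deviations under SAP section 4. Criterion 5 accepts the earlier value, so such patients meet the criteria, and the primary population is all enrolled subjects.
- A reader might infer that a fresh Visit 1 sample cures the problem. Step 7 shows that it generally does so only in part, and only for some patients.

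**Conclusion.** The concern holds. Selection on the outcome, one arm and a change-from-baseline estimate together imply some fall with no effect, and neither document corrects for it or mentions it.

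The size cannot be derived from the documents. About 0.13 to 0.40 points rests on assumed unselected means and SDs, normality, the qualifying value serving as baseline, and the whole planned SD of change being within-patient variation. Relaxing the last assumption lowers it. In checks with skewed distributions, the formulas overstated the artefact by up to about 0.03.

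One might conclude that the whole planned fall is artefact. The documents do not support that: only the extreme case (mean 8.0, SD 1.2) reaches about 0.4, and a source population mostly well above 7.5% would give a small artefact.

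The baseline definition is a genuine inconsistency between the two Visit 1 texts, but a secondary one. The changes are worth making because they are cheap and affect how the primary result will be read.

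**What to change.** **(a) Define the baseline.** In Protocol 7.5, reconcile Table 1 item 4 with Visit 1 item 4 so that an earlier value serves eligibility only. Enter the center-laboratory Visit 1 value, taken before training, in its own eCRF field, and record which value qualified the patient. In SAP 5.2.2, name that Visit 1 value as the HbA1c baseline.

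**(b) Limit the attribution.** In SAP 5.2.2, report an observed before-after change, not the effect of training alone. Make the same change wherever the effect wording recurs: the objectives (Protocol section 6, SAP 1.2) and SAP 5.2.3, 5.2.4, 5.2.6 and 5.2.7.

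**(c) Add a sensitivity table to SAP 5.2.2**, not a pass/fail gate. With D = baseline mean − assumed unselected mean, using each group's own baseline mean:
- qualified on the Visit 1 value: (1 − rho) × D;
- qualified on an earlier value: ((r1 − rho)/r1) × D.

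Weight the two groups by patient numbers. Restrict rows to means and SDs that fit the observed baseline mean and spread above the 7.5% cut, and to rho values compatible with the observed SD of change. Without this restriction the rows become inconsistent. For example, a baseline mean of 9.215 with rho 0.7 gives 0.36, 0.21 and 0.06 for assumed means of 8.0, 8.5 and 9.0, but the first and last need unselected SDs of about 1.90 and 1.15, outside the 1.2 to 1.8 considered here.

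SAP section 4 needs no change.

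**Cost.** At most one routine HbA1c test for patients who qualified on an earlier value (none if Visit 1 item 4 already requires it), two eCRF fields, and protocol and SAP text. The table rests on stated assumptions and does not identify a training effect.

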7.4. Patient information and obtaining informed consent

Before executing any study procedure, the informed consent of the patient must be obtained. The following steps must be taken in order to obtain the informed consent of the patient for participation in the study.

1. Physician-investigator must ascertain whether patients understand and read Russian.
2. Patient receives information about the study, its objectives, a brief description of the study design and the patient requirements in case he/she consents to participate in the study. Patients are informed that they meet the criteria required for study entry.
3. Patient takes his/her time to ask questions, discuss the study with family members and take a decision about study participation before the next visit to the medical center. If the patient gives his/her consent to participate in the study, the next visit is scheduled within 5 days from the moment of signing the informed consent form by the patient.
4. Patients are informed that they are entitled to change their mind and withdraw from participation at any time, and this will not affect their treatment in any way.

A patient is considered to be enrolled in the study when he/she signed the Informed Consent Form.

7.5. Stages of the clinical trial.

The enrolment period of the trial will be approximately 1 month, The follow-up period for each patient is 6 months. A total of maximally 90 patients will be included in the trial, to allow for 73 evaluable subjects at 6 months follow up, which is due to the statistical calculation of the required number of patients (see section 10 of this protocol).

The study design and calendar of events, including all the necessary visits, their order, appointment time and manipulations carried out during the visits, are presented in Fig. 2 (Study Flow) Table 1 (Study design) and Table 2 (Calendar of events).

[figure not shown]

Fig. 2. Study Flow

Table 1. Trial design

Patient selection and start		Interim control (telephone)	Interim control (3 month FU visit)	Completion and evaluation
Visit 1 (Screening) duration - 5 working days	1 Patient evaluation in terms of his/her possible participation in the study. For female patients: perform a pregnancy test	1 Make sure that patient follows study protocol: uses supplied needles only once, and watches recommended video lessons	1 Enter data regarding HbA1c and insulin TDD	1 Enter data regarding HbA1c and insulin TDD
	2 Obtaining the informed consent	2 Evaluate current level of glycemic control and cases of hypoglycemia	2 Evaluate current level of glycemic control and cases of hypoglycemia.	2 Evaluate current level of glycemic control and cases of hypoglycemia.
	3 Assignment of participant identification number (code)	3 Find out about current level and frequency of measuring blood glucose and insulin TDD.	3 Examine injection sites and injection technique, size and localization of lipohypertrophy	3 Examine injection sites and injection technique, size and localization of lipohypertrophy
	4 Fill in the questionnaire, enter data regarding HbA1c and insulin TDD. Note: the HbA1c value may be measured at screening or the latest measured value (max. 30 days prior to screening) may be taken.	4 Make sure that the patient follows the recommended injection technique, correctly alternates injection sites and avoids injections into sites of lipohypertrophy. Remind the patient to use the BGM and complete the diary.	4 Enter data regarding possible AE	4 Collect diary and review completion
	5 Examine injection sites and injection technique, size and localization of lipohypertrophy (if applicable).	5 Enter patient's answers in the interim control form	5 Review diary completion	5 Request patient to complete the EQ-5D questionnaire
	6 Evaluate current level of blood glucose and cases of hypoglycemia.	6 Remind patient about next personal visit	6 Download the data from the BGM to a PC for further statistical analyses.	6 Arrange subsequent medical follow-up for the patient, if required
	7 Carry out personalized training on correct injection technique	7 Enter data regarding possible AE	7 Provide new supply of BD Micro-Fine Plus 4 mm 32G needles (3 months' supply) and additional strips and lancets for BGM.	7 Release patient from participation in the study (fill in Exit from study form).
Follow-up visits – visit №2, and 4 (by phone) in 45 and 135 days +/-10 days after visit 1		Follow-up visit – visit №3 (personal) in 90 days +/-10 days after visit 1		Visit 5 (personal, final) in 180 days +/-10 days after visit 1

8 Familiarize patient with distance education resource and recommend independent studies using video lessons		8 Schedule the HbA1c test and next personal visit in 90 days. Schedule next telephone follow up (visit 4)	8 Download the data from the BGM to a PC for further statistical analyses.
9 Request patient to complete the EQ-5D questionnaire			9 Enter data regarding possible AE
10 Provide patient with required supply of BD Micro-Fine Plus 4 mm 32G needles (3 months' supply).			10 Collect the BGM from the patients. Complete the log forms
11 Schedule the HbA1c test and next personal visits in 90 and 180 days, and over-the-phone visits for interim control in 45 and 135 days.			
12 Provide patients the diary and a Blood Glucose Meter (BGM) with strips and lancets (3 months' supply). Explain how to complete the diary and use BGM.			
13 In a week +/-2 days after the screening visit, the investigator must ascertain if patient viewed recommended lessons.			

Visit № 1 – screening visit (personal visit).

1. For study purposes, prior to patient enrolment a physician will interview the patient about his/her condition in order to evaluate the effectiveness of current practices in terms of injection technique, the finding of gaps and possibilities for their improvement. Depending on the results of such an evaluation, the investigator will offer the patient familiarization with the corresponding distance learning modules.
2. Information about study participation is provided, and the informed consent form is signed.
3. Collection of the patient's demographic data and medical history data is carried out. The patient undergoes a physical examination to make sure that he/she meets the inclusion/exclusion criteria. A urine pregnancy test must be done for the childbearing potential female patients.
Examination of injection sites and injection technique is performed. The presence of lipohypertrophy is determined, and lipohypertrophy areas are marked on the diagram, indicating their number and size.
4. A physician makes an arrangement for the glycated hemoglobin test (HbA1c), which is carried out in the laboratory of the center participating in a given clinical trial at investigator's place of work.. To verify the inclusion criteria, the HbA1c value may be measured at screening or the latest measured value (max. 30 days prior to screening) may be taken. The result should be entered in the eCRF.
5. The current level of blood glucose and cases of hypoglycemia will be evaluated during the visit and the patient will be asked about his/ her condition and data will be completed in the eCRF.
6. The insulin dose of the day prior to the visit (basal and boluses) will be captured in the eCRF.
7. A theoretical course is given on lipohypertrophy and the necessity of alternating the injection sites, followed by hands-on classes on insulin injection technique. Also, patients are familiarized with other aspects of insulin therapy. Patients are given instructions that, in case of necessity, they can change the insulin dose during the clinical trial. The patient is not recommended to change the long-acting and intermediate-acting insulins, and not to change insulin subgroups, i.e., short-acting and ultra short-acting insulins.
8. The patient is familiarized with the structure and scope of the distance learning program. The whole course of video lessons will be recommended to the all patients for individual studies independently from their insulin injection technique success.
9. Patients are requested to complete the EQ-5D questionnaire, see Appendix B for an example.
10. Patients are supplied with an information package – booklet with instructions how to practice the right injection technique, rotation grid, the information letter for a physician in a local outpatient hospital to inform the patient is participating in the clinical trial. The letter should be formalized on the formal paper of the site. Guidelines on video lessons and web access codes, if required.
11. Patients will also receive:
 - a. disposable BD Micro-Fine 32G (0.23mm/32G x 4 mm) needles in the amount

required for 3 months (Table 3),

- b. Blood Glucose Meter (BGM), strips and lancets in the amount enough for 400 measurements, which corresponds with 100 days (approx. 3 months) of 4 measurements per day,
- c. a patient's diary. Patients are requested to record their insulin doses and if they experienced any adverse effects, including hypoglycemia's.

12. Patients must be informed to return the BGM back to the site after the study. Boxes of needles, boxes of strips and lancets will be marked: "BD property. Only for clinical trial. Not for sale". Glucometers will be marked: "BD property. Only for clinical trial. Not for sale. Must be returned".

13. Patients are instructed how to use the BGM and its accessories, how to complete the patient's diary. BGMs will be calibrated if needed and the date and time will be set correctly. Patients will be recommended to make at least 4 measurements of glucose per day by the provided BGM regardless of the type of diabetes: 3 before meals (one of which is before breakfast) and one measurement before bedtime. More measurements may be performed in accordance with clinical practice. The recommended measurements as listed above should be performed during the following time periods:

- a. within 2 weeks after screening,
- b. the last 2 weeks before the visit of the 3rd month, and
- c. the last 2 weeks before the visit of the 6th month.

The rest of the time, the patient may measure the level of glucose in the blood in accordance with accepted clinical practice.

During the same 2 weeks periods the patient is asked to complete the diary with basal and bolus insulin doses on a daily basis. Also, the patient has to complete the diary with all episodes of hypoglycemia.

14. The next meeting with the physician-investigator is scheduled in 90-100 days (visit № 3), as well as the interim visits, which include phone contacts in 45 +/-10 days (visit № 2) and in 135 +/-10 days (visit № 4).
15. A preliminary scheduled blood test for glycated hemoglobin takes place in 90 +/-10 days as well as in 180 +/- 10 days after the screening visit, to be carried out in the laboratory of the center participating in a given clinical trial at the investigator's place of work. The test must be done not sooner than a week before the study completion visit or on the day of the completion visit.
16. The Investigator informs the patient they have to visit the investigator before the next scheduled personal visit in case they do not have sufficient strips. Also, the patient can visit the investigator personally instead of the phone visit if the patient realizes they do not have enough strips to cover the period until the next scheduled personal visit. In this case, the patients have to bring the diary and his BGM for the visit and the Investigator will download the data from BGM and return it back to the patient. The diary will be kept by the investigator and the patient will receive the new diary. The patient also will receive the required number of strips in amount enough to the next scheduled personal visit.

1-week visit (optional, phone).

In 1 week +/- 2 days after the visit № 1, the investigator must be sure that the patient has viewed the recommended video lessons. To this end, the Sponsor provides the investigator with the report on the patient's use of the education resource. If the patient has not viewed recommended video lessons, then the investigator reminds him about the necessity of viewing the recommended video lessons. The information about video lesson viewing is marked in the patient's eCRF.

Visits № 2 and № 4- follow-up visits (over-the-phone visits, or personal visit).

1. The interim contacts with the patient are maintained over the phone in 45 +/-10 days and 135 +/-10 days from the first visit, with the view to evaluate the patient's adherence to the study design, review diary completion and to provide recommendations on the correction of the injection technique, as well as to evaluate the progress of his/her distance learning.
2. Information on the patient's glycemic control (glucose level), total daily insulin dose (the day prior to the phone visits) and hypoglycemic events since the last visit is requested and the information is entered in the eCRF.
3. To remind the patient to bring the BGM back on the next personal visit and to remind the patient on the appointment for having the HbA1c test, as was scheduled on the first and third visit
4. Data regarding possible AEs is collected in a special form of the patient's eCRF.
5. In case of the occurrence of adverse events (AE) in the course of the study after the screening visit, the investigator will record these in a special form (eCRF). In case of serious adverse events (SAE), the corresponding eCRF must be filled in and the event reported to the Sponsor and to the corresponding Ethics Committee within 2 working days after the investigator has become aware of the event.
6. The investigator has to remind the patient to measure their glucose levels upon the protocol requirements and complete the diary with insulin doses 2 weeks before the next personal visit. The same reminder will be also done 2 weeks before or even earlier the next personal visit.
7. The Investigator informs the patient they have to visit the investigator before the next scheduled personal visit in case they do not have sufficient strips. Also, the patient can visit the investigator personally instead of the phone visit if the patient realizes they do not have enough strips to cover the period until the next scheduled personal visit. In this case, the patients have to bring the diary and his BGM for the visit and the Investigator will download the data from BGM and return it back to the patient. The diary will be kept by the investigator and the patient will receive the new diary. The patient also will receive the required number of strips in amount enough to the next scheduled personal visit.

Visit № 3 – follow-up visit (personal).

1. The physician-investigator enters the latest results of the glycated hemoglobin (HbA1c) measurements and insulin TDD (basal and boluses of the day prior to the visit) in the patient's eCRF.
2. The data, saved in the patients' BGMs should be downloaded by the investigator. The

downloaded data will be transmitted to the Sponsor for analysis. The data will be transferred for analysis and storage to Becton, Dickinson and Company in the United States of America.

3. The existing level of glycemic control and cases of hypoglycemia since the last visit are assessed.
4. The physician conducts an examination of the injection sites and the injection technique, the size and localization of lipohypertrophy (if present).
5. The physician will collect and review correct completion of the diary and will provide the patient with a new diary.
6. Data regarding possible AEs is collected in a special form of the patient's eCRF. If necessary, a subsequent medical follow-up is arranged for the patient.
7. Patients will receive a new batch of 32G (0.23mm/32G x 4 mm) needles, BGM strips, and lancets for the next 3 months of the study.
8. Confirm the telephone follow up at Day 135 +/-10 days (visit № 4).
9. Confirm appointment to measure HbA1c for visit № 5 (6 months follow up).
